5. STUDY INTERVENTIONS

5.1 Interventions, Administration, and Duration

Subjects will be randomized to receive either a “standard visit” or an “expanded visit” with a study provider. The standard visit is based on a high quality, empathic, conventional primary care encounter. The expanded visit is based on an integrative medicine consultation. Both visits are based on a script of questions and statements to the patient/subject (see Appendix E). The standard visit script includes questions about GERD history, symptoms, prior evaluation and treatments, and past medical history as well as a brief physical exam. The expanded visit script includes the same questions as the standard visit script plus additional questions that inquire about the modalities of their GI symptoms (e.g., nature of the reflux taste, sensation of heartburn pain and/or abdominal fullness, time of day better/worse), details about non-GI symptoms, quality of sleep, the effect of the weather on symptoms, food cravings and aversions, menstrual flow, fears/phobias, and overall temperament. In this way, the expanded visit tries to understand the patient’s/subject’s constitution in a way that many systems of integrative medicine attempt to do. To reduce the potential for introducing bias by using the words “standard” and “expanded”, the visit templates that the study providers will follow will simply refer to the number of questions to be asked on the template (e.g., 6 Question Template).

At the end of both the standard and expanded visits, the provider will recommend the subject take the study medication and describe how to take it and what to expect. Subjects will receive the same scripted advice in both groups. Each subject will receive an 8-week supply of amitriptyline or omeprazole with instructions for how to take it (10 mg daily at bedtime or 20 mg daily when waking up, respectively).

In our pilot study⁶⁴ we did not limit the amount of time spent with the study subject. On average, the standard visit lasted 18 minutes (range 11-32 minutes) and the expanded visit lasted 42 minutes (range 23-74 minutes). The study providers will be instructed to maintain equal empathy in both groups (e.g., kind and friendly manner, maintain eye contact, active listening and repeating back the patient’s words, expressions of empathy). Thus, the main differences between the visits will be the length of time spent with the subject and the additional questions that are asked.

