6.2.5 Post-Intervention Measures (Day 0)

Immediately following the study physician visit, subjects will be asked to complete the following questionnaires:

- Impressions of the Study Physician questionnaire – a 4 item measure assessing the patient’s impression of the study physician including overall rating of the physician, satisfaction with the physician, willingness to recommend the physician to others, and desire to see the physician again.
- Consultation and Relational Empathy questionnaire (CARE) – a validated and commonly used 10 item measure for assessing the quality of the patient encounter and perceptions of empathy from the treatment provider⁸⁰. I used it in my pilot study.
- HEAL Patient-Provider Connection – a subset of the Healing Encounters and Attitudes, a recently validated 7-item measure of the patient-provider connection. This is a patient-reported outcome developed as part of a set of tools to measure non-specific factors in treatment using the NIH PROMIS methodology⁸¹.
- Current Stress Question – 1 item self-report measure of current stress level on a scale of 0 (no stress) to 10 (extreme stress)

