9.5 Outcomes

A combination of description statistics, pearson correlations, and general linear models (GLM) such as ANCOVA, will be used for analyzing the data.

Assessment	Time Points Collected	Analysis Plan	Section
Demographics, health behaviors, height & weight	Visit 1	Descriptive statistics	9.6
Daily GERD Symptom Diary	Visit 1 & Visit 2	Primary Outcome – ANCOVA analysis adjusting for baseline GERD symptom severity and visit type using follow-up GERD symptoms as the outcome.	9.5.1
GERD-HRQL	Visit 1 & Visit 2	Descriptive statistics and secondary measures of GERD symptom severity in ANCOVA analyses.	9.6
NIH PROMIS GERD			
GSRS			
Current Stress	Visit 1 (both before & after provider visit) & Visit 2	Descriptive statistics and covariate in GLM analyses.	9.6
PSS-10	Visit 1 (before provider visit) & Visit 2	GLM to determine whether perceived stress is a modifying factor for change in GSR and HRV in the context of the visit intervention	9.6
FFI	Visit 1	GLM to determine whether personality is a modifying factor for change in GERD symptoms in the context of the visit intervention	9.6
GSR & HRV	Visit 1	Secondary Outcome – GLM assessing change in GERD symptom severity and physiologic concordance in patient-provider dyads	9.5.1
Video Recording	Visit 1	Secondary Outcomes - GLM to compare the frequency of supportive provider behaviors between the standard and expanded visit groups and responders vs. non-responders (those with a 50% or greater improvement in GERD symptoms).	9.5.2
Impressions of the Study Physician	Visit 1, post-intervention	GLM to determine whether empathy and the patient-provider connection modify change in GERD symptoms in the context of the visit intervention	9.6
CARE			
HEAL Patient-Provider Connection			

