9.5.1 Primary Outcome

1. Change in the average daily GERD symptom severity score from baseline to the last week of the study in the expanded vs. standard group. GERD symptom severity is based on the sum of scores assessing the severity of daytime heartburn, nighttime heartburn, and acid reflux each on a 0-4 point scale (none, mild, moderate, severe, very severe; higher scores signify worse symptoms). We will use ANCOVA for the primary analysis, adjusting for baseline GERD symptom severity and visit type assignment using the 8 week follow-up GERD symptom severity as the outcome. Potential moderators that will be assessed in exploratory analyses will include gender (both patient and provider), race, visit length, patient stress, personality type, and perceived connection with/empathy of the provider.

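### Exploratory moderator analyses use visit length and post-visit empathy ratings, which the randomised visit itself produces, and the stress covariate has no stated time point

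*Combined protocol and SAP*

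**What the plan says.** Section 9.5.1 specifies the primary ANCOVA with baseline severity and visit type, then turns to exploratory work: "Potential moderators that will be assessed in exploratory analyses will include gender (both patient and provider), race, visit length, patient stress", followed by "personality type, and perceived connection with/empathy of the provider". The table in section 9.5 gives the same role to the Impressions of the Study Physician, CARE and HEAL questionnaires: "GLM to determine whether empathy and the patient-provider connection modify change in GERD symptoms in the context of the visit intervention". Section 9.6 again lists perceived empathy among the factors that may modify improvement.

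Section 6.2.5 dates those three questionnaires: "Immediately following the study physician visit, subjects will be asked to complete the following questionnaires". On length, section 5.1 says that "the main differences between the visits will be the length of time spent with the subject and the additional questions that are asked".

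Current Stress is collected before the provider visit, after it and at Visit 2. Its entry in the 9.5 table reads "Descriptive statistics and covariate in GLM analyses", with no time point or model named. Patient stress in the 9.5.1 moderator list is also undated, although section 9.5.2 does name baseline perceived stress for the GSR and HRV analysis.

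**The concern.** A moderator analysis asks whether the effect of assignment differs between kinds of patient, where the kind is fixed before assignment. Visit length and the ratings of the provider do not meet that condition. Length is part of what is being randomised, and Secondary Objective 2 expects the expanded visit to improve the interaction that the ratings measure.

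Within a stratum of such a variable, the two arms hold differently selected patients. In the pilot, a 30-minute visit would have been 12 minutes above the standard average of 18 and 12 minutes below the expanded average of 42. A standard-arm patient with an unusually long visit would be set against an expanded-arm patient with an unusually short one. A difference between them mixes the visit effect with whatever made one visit run long and the other short.

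At stake is the reading of the exploratory results on what makes a longer visit work, which section 2.2 says should guide later changes to the intervention. Calling the analyses exploratory lowers the claim made for them but does not make the comparison valid.

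**Working it through.** **1. The plan's own figure.** Inputs from section 9.2: 30 per arm, 80% power, two-sided alpha 0.05, SD 1.5, 2.0 and 2.5. A two-sample t-test (noncentral t, 58 df) gives minimal detectable differences of 1.103, 1.471 and 1.839, which match the stated 1.10, 1.47 and 1.84. The primary model contains only baseline severity and visit type, so these figures do not depend on the variables discussed here.

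**2. Timing against role.**

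| Variable | When it arises | Role in the plan |
|---|---|---|
| Gender, race, NEO-FFI | before randomisation | moderator |
| PSS-10 | before the visit and at Visit 2 | moderator (baseline named only in 9.5.2) |
| Visit length | during the randomised visit | moderator |
| Impressions, CARE, HEAL | after the visit | moderator |
| Current Stress | before the visit, after it, and at Visit 2 | covariate, time point not stated |

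**3. How far the arms overlap on visit length.** Pilot figures from section 5.1: standard mean 18 minutes (range 11 to 32), expanded mean 42 (range 23 to 74). The ranges share only 23 to 32 minutes. Within-arm SDs are not given, so they are assumed as a fraction of the range (21 and 51 minutes). With 1:1 allocation and a mean difference of 24, the share of length variance explained by visit type is

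R² = (24²/4) / (24²/4 + mean within-arm variance) = 144 / (144 + mean within-arm variance).

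- SD = range/3: 7.0 and 17.0; mean variance (49 + 289)/2 = 169; R² = 144/313 = 0.46.
- SD = range/4: 5.25 and 12.75; mean variance 95.06; R² = 144/239.06 = 0.60.
- SD = range/6: 3.5 and 8.5; mean variance 42.25; R² = 144/186.25 = 0.77.

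**4. What conditioning does to the visit coefficient.** Take a linear model with negative values meaning lower follow-up severity in the expanded arm. Visit type shifts the mediator by a (in within-arm SD units). The mediator acts on the outcome with slope b, and the direct effect is c, so the total effect is c + ab. With no common cause of mediator and outcome, the visit coefficient given the mediator is c. For a total effect of −1.10 it is −0.55 if half the effect passes through the mediator, and 0 if all of it does.

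Now add an unmeasured common cause with loading λ on the mediator and k on the outcome. The adjusted visit coefficient becomes c − akλ, and the mediator slope becomes b + kλ. For illustration: a = 1, b = c = −0.55, λ = 0.3, k = −0.3 × 1.5 = −0.45, so kλ = −0.135. The adjusted visit coefficient is −0.55 + 0.135 = −0.415. A simulation of 400,000 subjects gives −0.42. That is neither the total effect (−1.10) nor the direct effect (−0.55). The unadjusted estimate stays at −1.10.

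**5. The same term enters a mediation analysis.** With the inputs of step 4, the estimated indirect effect is 1 × (−0.55 − 0.135) = −0.685 against a true −0.55. Relabelling these variables as mediators therefore asks the right question but does not remove the confounding.

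**The case against.** The strongest reply is that nothing confirmatory is touched, and that stands. A reader might infer that the trial's estimate of the visit effect is biased. It is not: the primary ANCOVA excludes all of these variables, and an effect carried wholly by empathy would still appear there.

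A reader might also infer that the plan adjusts for post-visit stress. The documents do not say so. They leave the time point open, and the one analysis that dates perceived stress uses baseline.

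Nor can it be said that the mechanism question is missed. Section 9.5.2 compares coded behaviours across visit types, uses the concordance index with visit type and/or symptom severity, and relates behaviours and GSR or HRV change to symptom change. Only an estimate of the indirect effect is absent.

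It is tempting to go further and quote a loss of power. With range/4 SDs, the variance inflation is 1/(1 − 0.602) = 2.51, the standard error rises by √2.51 = 1.59, and power for 1.10 at SD 1.5 falls from about 80% to about 43%. That supposes a model with visit type and length side by side and length unrelated to outcome within arm. The plan describes no such model; a moderator implies an interaction. A reversed sign for the visit effect can be produced by simulation, but only with mediated shares and confounder strengths that the documents do not supply.

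Finally, section 5.1 tells providers to keep empathy equal between arms, so the visit may shift perceived empathy only a little. This makes the size uncertain for CARE, HEAL and Impressions. It does not change their timing, and it does not apply to visit length.

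**Conclusion.** The point holds for the exploratory analyses in section 9.5.1, the 9.5 table and section 9.6. Visit length and the patient's ratings of the provider are consequences of the randomised visit and cannot serve as moderators of its effect. Interaction or adjusted models using them are not valid subgroup analyses, and their visit coefficient should not be read as the effect of assignment. The missing time point for Current Stress leaves post-visit adjustment possible. The primary test and its design figures stand.

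That the arms overlap little on length follows from the pilot means and ranges. The 46% to 77% figure rests on assumed SDs of range/3 to range/6. The size of any distortion cannot be taken from the documents, and the coefficients in steps 4 and 5 of the working are illustrations. The change is worth making because these analyses bear on the trial's mechanistic aims.

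**What to change.** In sections 9.5.1, 9.5 and 9.6:

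- Limit moderator analyses to variables fixed before randomisation: patient and provider gender, race, NEO-FFI, baseline PSS-10 and pre-visit Current Stress.
- State that any visit-effect model using Current Stress as a covariate uses the pre-visit value only.
- Move visit length, Impressions, CARE, HEAL and post-visit stress to an exploratory mediation analysis: the effect of visit type on the mediator, the mediator–outcome association given visit type and baseline severity, and the indirect effect with a bootstrap interval.
- State the assumption of no unmeasured confounding between mediator and outcome, and add a sensitivity analysis that varies its strength, since this regression is exposed to the bias shown in step 5 of the working. For visit length, note the limited overlap between arms.
- Report the results as hypothesis-generating, given low precision at 60 subjects.

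The cost is SAP wording and a small amount of extra analysis. No new data are needed, and the primary analysis and sample size do not change.

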2. To identify patient and physician behaviors associated with GERD symptom improvement.

Design and Outcomes

This is a randomized controlled trial to assess the physiologic and behavioral mechanisms associated with augmented medication effects in adult patients with functional GERD-related symptoms.

Subjects will be randomized to receive one of two different semi-scripted visit types – either a “standard visit” modeled after an empathic, conventional primary care evaluation or an “expanded visit” modeled after an integrative medicine consultation. During the visit, we will measure heart rate variability (HRV) and galvanic skin response (GSR) in the patient-provider dyads; in addition, we will video record the interactions for later

analysis of behavioral responses. Subjects will receive a two-month supply of amitriptyline (10 mg/day) or omeprazole (20 mg/day, depending upon the nature of their GERD symptoms), along with instructions for taking it. Following the visit, subjects will complete questions assessing their relationship/rapport with the study provider. Subjects will complete a daily GERD symptom diary during the first and eighth weeks of the study. At the end of the 8-week observation period, they will complete follow-up measures of GERD symptom severity and quality of life.

Interventions and Duration

Subjects will have a single visit with a “study provider,” a physician or nurse practitioner who they have never previously met. Subjects will complete a daily symptom diary for the 1st and 8th weeks following this visit and return for a second study visit in which they will complete questionnaires and be debriefed by a member of the study team.

Sample Size and Population

We plan to enroll 60 subjects with functional GERD, age 24-70 with heartburn symptoms 3 or more days per week. Thirty subjects will be randomized to the expanded visit intervention and 30 subjects will be randomized to the standard visit intervention (1:1 expanded vs. standard randomization). We will also enroll approximately 5-6 physicians or nurse practitioners and stratify randomization by study provider such that each provider will see 10-12 subjects (5-6 expanded visits and 5-6 standard visits).

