3. STUDY DESIGN

Study design: Single-center, single-blind, randomized controlled trial

Primary outcome:

1. Change in the average daily GERD symptom severity score from baseline to the last week of the study in the expanded vs. standard group. GERD symptom severity is based on the sum of scores assessing the severity of daytime heartburn, nighttime heartburn, and acid reflux each on a 0-4 point scale (none, mild, moderate, severe, very severe; higher scores signify worse symptoms).

Secondary outcomes:

1. Ratio of the sum of positive correlations over the sum of negative correlations in GSR (or HRV) across patient-provider encounters for standard vs. expanded visit types and for responders vs. non-responders (those with a 50% or greater improvement in their GERD symptom severity).
2. Absolute change in GSR (or high frequency HRV signal) in patient recordings from the beginning of the study visit to the end of the study visit and correlation with subsequent change in GERD symptom severity.
3. Differences in blinded ratings of 2 minute thin slices of study visit videos from the beginning to the end of the study in supportive global impressions (e.g., engagement, relaxed, patient seems pleased/satisfied) and non-verbal behaviors (e.g., smiling) between standard and expanded visit types and correlation with subsequent change in GERD symptom severity.

Study population:

Men and women age 24-70 with heartburn symptoms 3 or more days per week not responsive to proton pump inhibitors or with known functional heartburn. We will enroll until we reach 60 completing subjects.

Study location:

University of California Davis Medical Center

Length of subject participation: 8 weeks

Length of study enrollment: 2 years

Groups:

- 1) Standard visit (n=30), modeled after an empathic, high quality conventional primary care visit.
- 2) Expanded visit (n=30), modeled after a visit with an integrative medicine provider

Randomization:

The randomization code will be generated by the study statistician as described below (sections 4.3 and 9.2). The study will be single-blinded (study providers and the research team will know what the subject is receiving but the subject will not). Randomization will be stratified based on study provider. We anticipate 5 or 6 providers each seeing 10-12 subjects (5-6 standard visits, 5-6 expanded visits).

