- Interpersonal Reactivity Index (IRI) – a validated 28 item self-assessment of cognitive and affective components of empathy⁷⁸.
- NEO Five Factor Inventory (NEO-FFI) – a validated 60 item instrument that measures five major dimensions of personality: extraversion, neuroticism, agreeableness, conscientiousness, and openness to experience [73]. Some dimensions have been associated with response to enhanced patient-provider interactions in others' studies⁷⁷.
- Demographics and practice – will assess things such as age, gender, race/ethnicity, and clinical experience (see Appendix D).
- Current Stress Question – 1 item self-report measure of current stress level on a scale of 0 (no stress) to 10 (extreme stress). Study providers will complete this question immediately prior to each study subject visit.
- Perceived Stress Scale (PSS) – a widely used 10 item measure of perceived stress that has been shown to correlate with a variety of different health outcomes⁷⁵. Study providers will complete this questionnaire immediately prior to each study subject visit.
- Fatigue Scale – 1 item self-report measure of the current fatigue level on a scale of 0 (no fatigue) to 10 (extreme fatigue). Study providers will complete this question immediately prior to each study subject visit.
- Physician Satisfaction Questionnaire (PSQ) – 20 item self-report measure assessing physician satisfaction with the patient visit. This measure includes a global satisfaction question and 19 items assessing 4 other domains: satisfaction with the patient-physician relationship, with the data collection process, with the appropriateness of the use of time, and with the absence of excessive demands on the part of the patient. Study providers will complete this questionnaire immediately after each study visit⁷⁹.

Randomization

Subjects will be randomized on the day of their baseline visit (Visit 1) to receive either the standard or expanded visit with the specific provider that they are scheduled to see that day. We will stratify randomization by provider so that each provider does the same proportion of standard and expanded visits. Randomization will occur during or immediately after subjects have completed their baseline questionnaires, immediately prior to the study visit.

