9.2 Sample Size and Randomization

The combined standard deviation (root mean square error) in my pilot fellowship study was 1.5⁶⁴. We are conservatively assuming that this number will likely be larger in this study given the greater number of providers involved. Given 30 subjects in each group (n=60 total), 80% power, a two-sided significance test with alpha = 0.05, the minimal detectable difference (MDD) in GERD symptom severity scores between the standard and expanded groups given the estimated standard deviations (SD) is shown in the adjacent table. These MDD values are similar to those found in my fellowship study⁶⁴ and are clinically meaningful^{86,87}.

Minimal Detectable Difference Between Groups	
SD	MDD
1.5	1.10
2.0	1.47
2.5	1.84

Treatment Assignment Procedures

A randomization scheme will be devised before the start of the study by the study biostatistician who will retain the code and will be responsible for breaking the blind at the end of the study. We do not anticipate a need to break the blind during the study because we are not expecting serious adverse events to occur more frequently in one visit group than another. Randomization will be stratified by provider, with permuted block sizes of 2 and 4 with a goal to have 5-6 providers each see 10-12 subjects. If a provider cannot commit to this many visits, the study biostatistician may need to adjust the randomization scheme and we will consent additional providers.

The study biostatistician will enter the randomization scheme into REDCap and subjects will be randomized immediately prior to the study visit intervention.

If a subject drops out or is unable to complete the study, the statistician may need to rebalance the randomization scheme.

Subjects will be informed of their visit group assignment during the debriefing at the end of the second study visit.

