9.6 Data Analyses

We will perform descriptive statistics on the sample demographics similar to our prior paper⁶⁴ including age, gender, race, ethnicity, body mass index (BMI), smoking status, and current medication use for GERD symptoms. We will also assess whether perceived stress, perceived empathy (both patient and provider), personality type (five factor inventory), or demographic factors modify improvement in GERD symptoms using generalized linear models. We will use the GERD-HRQL, NIH PROMIS GERD, and GSRS as adjunct/corroborating measures of GERD symptom severity. Blood samples will be processed and stored at - 80°C for later omics-based analyses that will be the subject of a future grant/study.

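### Provider gender, and provider empathy if section 9.6 means the IRI, would be tested in patient-level models although only 5-6 providers carry these traits

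*Combined protocol and SAP*

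**What the plan says.** Section 9.5.1 lists exploratory moderators of the primary outcome that "assessed in exploratory analyses will include gender (both patient and provider), race, visit length", along with patient stress, personality and how the patient perceived the provider. Section 9.6 includes among its questions whether "perceived empathy (both patient and provider), personality type (five factor inventory), or demographic factors modify improvement in GERD symptoms using generalized linear models". It gives no instrument for empathy on the provider side and does not repeat the exploratory label.

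The only empathy measure that providers complete is the IRI, described in section 6.2.3 as a "validated 28 item self-assessment of cognitive and affective components of empathy". The provider schedule in section 6.1 marks it at enrollment only, so each provider has one score.

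On numbers, the Précis states: "We will also enroll approximately 5-6 physicians or nurse practitioners and stratify randomization by study provider". Section 3 adds: "We anticipate 5 or 6 providers each seeing 10-12 subjects (5-6 standard visits, 5-6 expanded visits". Section 9.2 allows the count to grow: if a provider cannot commit, "the study biostatistician may need to adjust the randomization scheme and we will consent additional providers".

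The models are general linear models (section 9.5) and generalized linear models (section 9.6). The primary ANCOVA adjusts for baseline severity and visit type. Provider is a randomization stratum, but no analysis includes a provider term, a random effect, clustered standard errors or provider-level degrees of freedom. Yet section 9.2, discussing the pilot SD, expects that "this number will likely be larger in this study given the greater number of providers involved".

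**The concern.** A trait that is constant within a provider is replicated only as often as there are providers. Comparing patients of male and female clinicians in a model with 60 independent rows treats 10-12 patients of one clinician as 10-12 separate pieces of evidence about gender. Any lasting difference between two or three clinicians, whatever its cause, then feeds directly into the gender coefficient and is judged against patient-level noise. An ordinary difference between individuals could be reported as an effect of provider gender or of provider empathy.

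Two different tests are in play and have to be kept apart. Section 9.6, read literally, asks whether a trait changes improvement, which is a main effect of the trait. Moderation of the expanded-versus-standard contrast, the natural reading of section 9.5.1, is a trait-by-visit interaction. Each provider delivers both visit types, so clustering affects the two tests differently.

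**Working it through.** **Inputs from the documents.** n = 60, 30 per arm, SD 1.5, 2.0 or 2.5 (section 9.2); 6 providers with 10 patients or 5 with 12, half of each visit type (section 3).

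**Assumptions.** The documents give neither an ICC nor a between-provider SD of the visit effect. The ranges used are ICC 0 to 0.10 after baseline adjustment, and a visit-effect SD between providers (τ) of 0, 0.5 and 1.0 points with outcome SD 2.0.

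**Step 1: the plan's own figure.** Section 9.2 reads: "Given 30 subjects in each group (n=60 total), 80% power, a two-sided significance test with alpha = 0.05, the minimal detectable difference" is tabulated as 1.10, 1.47 and 1.84. A two-sample t calculation with standard error SD × √(2/30) and 58 df gives 1.103, 1.471 and 1.839. The table reproduces. It covers the visit comparison only; no figure is given for any moderator.

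**Step 2: degrees of freedom.** A patient-level model with intercept, baseline, visit and trait leaves 60 − 4 = 56 df, or 55 with the interaction. At provider level a single trait leaves K − 2 = 4 df (6 providers) or 3 df (5 providers).

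**Step 3: trait's effect on improvement.** Design effect DE = 1 + (m − 1) × ICC. The patient-level standard error is too small by a factor √DE, and the actual error is about 2 × [1 − Φ(1.96/√DE)].

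| m | ICC | DE | √DE | Approximate type I error |
|---|---|---|---|---|
| 10 | 0.05 | 1.45 | 1.20 | 10.4% |
| 12 | 0.05 | 1.55 | 1.25 | 11.5% |
| 10 | 0.10 | 1.90 | 1.38 | 15.5% |
| 12 | 0.10 | 2.10 | 1.45 | 17.6% |

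Simulation of the patient-level model under no trait effect, with provider splits 3 v 3, 2 v 4 and 2 v 3, agrees: 5% at ICC 0, about 10-12% at 0.05 and 14-18% at 0.10. A t-test on provider means holds 5% throughout.

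**Step 4: trait-by-visit interaction.** Each provider's own visit effect is a within-provider difference, so the provider intercept drops out. With intercept variance only, the simulated error is 4-5%.

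If the visit effect varies between providers with SD τ, the standard error is too small by about √[(τ² + w)/w]. Here w is the patient-level variance of one provider's visit effect.
- m = 10: w = 4 × (1/5 + 1/5) = 1.6. The factor is √(1.85/1.6) = 1.08 at τ = 0.5 and √(2.6/1.6) = 1.27 at τ = 1.0, giving about 7% and 12%.
- m = 12: w = 4 × (1/6 + 1/6) = 1.33. The factors are 1.09 and 1.32, giving about 7% and 14%.

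Simulation gives 6-7% and 10-13%. It is slightly lower because the patient-level residual absorbs part of τ².

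**Step 5: what 5-6 providers can show.** For a two-group trait such as gender, the smallest two-sided exact permutation p-value is 2/20 = 0.10 (3 v 3), 1/15 = 0.067 (2 v 4) or 1/10 = 0.10 (2 v 3). None reaches 0.05, whatever the ICC. With a provider-level t-test (3 v 3, SD 1.5), the detectable effect of the trait on improvement is 1.46 points at ICC 0, 1.75 at 0.05 and 2.01 at 0.10, against 1.10 in a patient-level analysis.

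**The case against.** The best defence is that section 9.5.1 calls these analyses exploratory, no aim or hypothesis mentions provider gender or the IRI, and the primary ANCOVA is untouched. All of that stands and limits the stakes. It does not correct a standard error.

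A second defence is that moderation means the interaction, where intercepts cancel. This also stands. A reader might infer that the standard errors are too small for every provider-trait test; for the interaction they are not, unless the visit effect itself varies between providers. Scripts, training and video review (sections 5.1 and 9.4) are meant to limit that variation, and the documents give no estimate of it. A fixed provider factor would also remove the Step 3 problem, because the trait main effect could then no longer be estimated. The plan names no such factor.

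A reader might infer that provider empathy is certainly affected. Empathy in section 9.5.1 is the patient's perception, and the section 9.5 table ties it to the Impressions, CARE and HEAL questionnaires, which each patient completes and which vary within provider. The IRI has no row in that table. Only the 9.6 wording could mean it.

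A reader might also count gender, two IRI components and five NEO-FFI dimensions as eight provider traits with a large family-wise error. The documents do not commit to this. The FFI row is timed at Visit 1, when patients complete the instrument; providers complete it at enrollment. No section says that provider personality will be tested.

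**Conclusion.** The point holds for provider gender, which is plainly planned, and conditionally for provider empathy, if section 9.6 means the IRI. The mismatch between about 55 and 3-4 degrees of freedom follows from the design alone. The size of the inflation rests on assumptions. For the trait's effect on improvement it needs an ICC above zero, which section 9.2 makes plausible without quantifying it. For the interaction it needs provider-by-visit variation, about which the documents are silent, and at τ = 0.5 the excess is small. Consenting a few more providers would ease the problem but not remove it. Even with correct standard errors, 5-6 providers cannot separate gender from everything else in which those individuals differ. The consequence is a misleading exploratory finding, not a flawed primary result.

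**What to change.** In sections 9.5.1 and 9.6:

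- List provider-level and patient-level modifiers separately.
- Name the instrument meant by empathy on the provider side in 9.6. If it is CARE or HEAL, list it as patient-level; if it is the IRI, as provider-level.
- For any provider-level trait, estimate mean improvement and the expanded-versus-standard effect within each provider, and plot these 5-6 estimates against the trait. Report them descriptively, without p-values from patient-level models.
- State that 5-6 providers cannot separate gender from other differences between providers, and that such results only generate hypotheses.

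A mixed model with a random provider-by-visit slope should not be the main remedy. With 6 providers of 10 patients and SD 2.0, the method-of-moments slope variance is zero or negative with probability P(F(5, 48) ≤ 1.6/(τ² + 1.6)). That is about 49% at τ = 0.5 and 31% at τ = 1.0, so the model would often fall back to roughly the patient-level analysis.

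The change needs wording only, with no new data. The small cost is that provider-trait results become descriptive.
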